**For cohort 9, the same randomization ratio (3:1) of AMG 890 to placebo will apply.**

In consideration of the DLRT recommendations and review of emerging safety and/or PD data, dose adjustments (if any) will be made by Amgen on a treatment cohort basis and not on an individual basis.

The study endpoints are defined in Section 13.1

## 6.2 Number of Sites

This study will be conducted at 3 to 10 sites in the US and Australia. Additional sites in the same or in other countries may be added as necessary to complete enrollment.

Sites that do not enroll subjects within 1 month of site activation for enrollment may be closed.

## 6.3 Number of Subjects

Participants in this clinical investigation are referred to as “subjects.”

The sample size is based on practical considerations. Sample size is discussed in Section 13.2. It is anticipated that an approximate total of █ subjects in a total of 9 cohorts will be enrolled in this study.

## 6.4 Replacement of Subjects

In the event subjects are enrolled, but are withdrawn prior to IP administration, a replacement subject may be enrolled in the subject’s place.

Additionally, subjects who are withdrawn from the study (Section 11) may be replaced at the discretion of the Amgen Medical Monitor in consultation with the investigator or designee. The replacement subject will be assigned to receive the identical treatment as the replaced subject, but will be assigned a replacement number associated with this new record. All data from the replaced subjects will be captured, identified, and kept in the clinical trial database.

## 6.5 Estimated Study Duration

### 6.5.1 Study Duration for Subjects

Subject participation will vary according to enrollment scheme. The duration of the follow-up period for each cohort was defined based on the simulation results from the population K-PD model describing the Lp(a) response to AMG 890 administration developed based on 57-day GLP repeat-dose cynomolgus monkey toxicology and PK/PD studies (Section 5.2.1). Data suggest that the lengths of study participation proposed will allow plasma Lp(a) levels to return at least to 80% of the baseline levels for each subject after administration across the proposed AMG 890 clinical doses.

For cohorts 1 and 2, planned subject participation will last up to 141 days, including a 28-day screening period prior to investigational product (IP) administration and on-study period (through the end of treatment visit) lasting 113 days.

For cohorts 3 to 7, planned subject participation will last up to 253 days, including a 28-day screening period prior to IP administration and on-study period (through the end of treatment visit) lasting 225 days.

For cohorts 8 and 9, planned subject participation will last up to 393 days, including a 28-day screening period prior to IP administration and on-study period (through the end of study visit) lasting 365 days.

For cohorts 1 to 7, the end of treatment visit will complete the subject's participation in this study unless a follow-up period is required. If there is a clinically significant clinical or laboratory abnormality that requires monitoring, subjects will be followed until resolution of the abnormality or until it is considered stable.

For cohorts 1 to 9, if at the end of treatment visit, the plasma Lp(a) level has not returned to  $\geq 80\%$  of baseline (mean of screening and day 1 predose), the follow-up period will be required.

The end of treatment visit for cohorts 8 and 9 will be the same as the end of study visit (day 365).

Subjects in cohorts 1 and 2 will return to the clinical study site approximately every 2 weeks until the Lp(a) level returns to  $\geq 80\%$  of baseline. Assessments during the follow-up period will include physical examination; vital signs; and collection of blood samples for chemistry, hematology, lipid, Lp(a), and biomarker development. When the protocol amendment 2 is implemented, the follow-up visits will continue approximately monthly, as needed, and will include only Lp(a) monitoring as described below for cohorts 3 to 7.

Subjects in cohorts 3 to 7 will return to the clinical study site for Lp(a) monitoring approximately monthly starting from when the site has been notified of the Lp(a) follow-up requirement until the Lp(a) level returns to  $\geq 80\%$  of baseline.

Lp(a) assessments in the follow-up period will be performed by Medpace.

**Primary Completion:** The primary completion date is defined as the date when the last subject is assessed or receives an intervention for the final collection of data for the primary endpoint(s), for the purposes of conducting the primary analysis, whether the study concluded as planned in the protocol or was terminated early.

The primary completion date is the date when the last subject has completed the assessments for day 365 of cohort 9.

If the study concludes prior to the primary completion date originally planned in the protocol (ie, early termination of the study), then the primary completion date will be the date when the last subject is assessed or receives an intervention for evaluation in the study (ie, last subject last visit).

**End of Study:** The end of study date is defined as the date when the last subject is assessed or receives an intervention for evaluation in the study (ie, last subject last visit), following any additional parts in the study (eg, follow-up period; long-term follow-up), as applicable.

## 7. SUBJECT ELIGIBILITY

Investigators are expected to maintain a screening log of all potential study candidates. Before any study-specific activities/procedure, the appropriate written informed consent must be obtained (see Section [14.1](#)).

### 7.1 Inclusion Criteria

A subject that has provided written informed consent may be eligible for inclusion in this study only if the following criteria are met:

- 101 Men and women with ages between 18 and 60 years old, inclusive, for cohorts 1 to 5; and with ages between 18 and 65 years old, inclusive, for cohorts 6 to **8**; **and with ages 18 and 70 years old, inclusive, for cohort 9**.
- 102 Plasma Lp(a):
  - $\geq 70$  nmol/L and  $\leq 199$  nmol/L for cohorts 1 to 5
  - $\geq 200$  nmol/L for cohorts 6 to 9
- 103 For cohorts 6 to 9, subjects who are on statin must be on a stable dose of the same statin for at least 6 weeks prior to enrollment, and plan to remain on a stable dose (ie, no change in medication or dosage) for the duration of the study
- 104 Body mass index (BMI)  $\geq 18$  and  $\leq 32$  kg/m^2, at screening, **for cohorts 1 to 8**; **BMI  $\geq 18$  and  $\leq 40$  kg/m^2, at screening, for cohort 9**.

105 Women must be of non-reproductive potential:

- Postmenopausal defined as:
  - Age  $\geq$  55 years with cessation of menses for 12 months or more, OR
  - Age  $<$  55 years and no spontaneous menses for at least 12 months, AND with a follicle-stimulating hormone level  $>$  40 IU/L or according to the definition of “postmenopausal range” for the laboratory involved, OR
- History of hysterectomy, OR
- History of bilateral oophorectomy

106 Men must agree to practice an acceptable method of effective birth control while on study or for 90 days after receiving investigational product (for subjects who withdraw prior to end of study). Acceptable methods of effective birth control include sexual abstinence; vasectomy; or a condom with spermicide (men) in combination with barrier methods (diaphragm, cervical cap or cervical sponge), hormonal birth control or IUD (female partner of male participant)

107 Men must be willing to abstain from sperm donation while on study or for 90 days after receiving investigational product (for subjects who withdraw prior to end of study)

## 7.2 Exclusion Criteria

A subject will not be eligible for inclusion in this study if any of the following criteria apply:

201 Currently receiving treatment in another investigational device or drug study, or less than 30 days or 5 half-lives (whichever is longer), since ending treatment on another investigational device or drug study(s) prior to receiving the first dose of investigational product

202 Women who are lactating/breastfeeding or who plan to breastfeed while on study or through 90 days after receiving investigational product (for subjects who withdraw prior to end of study)

203 Men with partners who are pregnant or planning to become pregnant while the subject is on study or through 90 days after receiving investigational product.

204 Positive pregnancy test at screening or at any pre-dose time point.

205 History or evidence of a clinically significant disorder, condition or disease (eg, symptomatic heart failure, documented previous myocardial infarction in the previous 12 months, active infection requiring antimicrobial therapy that will not be completed prior to randomization, or major surgery in the previous 3 months of screening) that, in the opinion of the investigator or Amgen Medical Monitor, if consulted, would pose a risk to subject safety or interfere with the study evaluation, procedures or completion. Exceptions include:

- Subjects with controlled and stable arterial hypertension, with a systolic blood pressure [SBP] < 150 mmHg or diastolic blood pressure [DBP] < 90 mmHg at screening and day -1 for cohorts 1 to 5 or day -3 to -1 for cohorts 6 to 9, with no change in medication and dosage for at least 6 weeks prior to enrollment, and expected to remain on this dose and medication for the entire duration of the study. Subjects not on medication are excluded from the study if systolic blood pressure [SBP] > 150 mmHg or diastolic blood pressure [DBP] > 90 mmHg at screening or day -1 for cohorts 1 to 5 or day -3 to -1 for cohorts 6 to 9. If the initial BP is elevated, the reading may be repeated again at least 15 minutes later and the lower of the 2 readings may be used.
- For cohorts 6 to 9, at least 6 subjects in each cohort with diagnosis of hyperlipidemia on treatment with a stable dose of the same statin (with or without concomitant ezetimibe) for at least 6 weeks prior to enrollment, and expected to remain on this dose and medication for the entire duration of the study
- **For cohort 9, diagnosis of diabetes is not excluded provided diabetes is well-controlled according to treating physician's assessment and discretion, and the subject is on stable doses of diabetes medications for at least 6 weeks prior to enrollment**

206 Planned elective surgery to occur at any time from screening visit through the end of treatment visit for cohorts 1 to 7, and through the end of study visit for cohorts 8 and 9

207 Estimated glomerular filtration rate (eGFR)  $\leq$  60 mL/min/1.73 m^2, as defined by the local laboratory, at screening

208 Triglycerides  $\geq$  5.65 mmol/L (ie, 500 mg/dL) at screening

209 History or clinical evidence of liver dysfunction, including total bilirubin  $>$  upper limit of normal (ULN) or ALT or AST  $>$  1.1 ULN of the laboratory's reference at screening or at day -1 for cohorts 1 to 5, or day -3 to -1 for subjects not on statin in cohorts 6 to 9. For subjects on stable dose of statin in cohorts 6 to 9, ALT or AST  $>$  1.5 ULN of the laboratory's reference at screening or at day -3 to -1.

210 History or clinical evidence of bleeding diathesis or any coagulation disorder, including prothrombin time (PT), activated partial thromboplastin time (aPTT), thrombin time (TT), or platelet count outside of the laboratory's normal reference range at screening

211 **For cohorts 1 to 8, history or clinical evidence of diabetes mellitus, including a fasting glucose  $\geq$  125 mg/dL (6.9 mmol/L) at screening**

212 History or clinical evidence of peripheral neuropathy

213 History of malignancy of any type, other than in situ cervical cancer or surgically excised non-melanomatous skin cancers occurring more than 5 years prior to randomization

214 Positive results for human immunodeficiency virus (HIV) antibodies, hepatitis B surface antigen (HBsAg), hepatitis B core antibody (HBcAb), or hepatitis C virus

ribonucleic acid (RNA). For hepatitis C, hepatitis C antibody (HepCAb) testing is done at screening, followed by hepatitis C virus RNA by polymerase chain reaction (PCR) if hepatitis C antibody is positive.

215 Subject was previously enrolled in this study or has been previously exposed to AMG 890

216 Use of any herbal medicines, vitamins or supplements known to affect lipid metabolism (eg, fish oils > 4000 mg/day, red yeast rice extract), within 30 days prior to dosing on day 1

217 All herbal supplements and nutritional supplements (with the exception of those known to affect lipid metabolism, which are excluded as above) taken within 30 days prior to dosing on day 1 and continued use, if appropriate, must be reviewed and approved by the investigator and Amgen Medical Monitor. Written documentation of this review and Amgen acknowledgement is required for subject participation.

218 Use of any over-the-counter medications within 14 days or prior to dosing on day 1. Exceptions are listed below:

- Acetaminophen (paracetamol), up to 2 grams per day for analgesia
- For cohorts 6 to 9, use of low-dose acetylsalicylic acid (up to 162.5 mg daily) is allowed, provided it is stable for at least 6 weeks prior to enrollment and is planned to be the same dose for the duration of the study

219 Use of any prescription medications within 14 days or 5 half-lives (whichever is longer), prior to dosing on day 1. Exceptions are listed below:

- Hormone replacement therapy (eg, estrogen, thyroid) provided subject is stable on replacement therapy
- Medication for the management of arterial hypertension, including but not limited to angiotensin-converting enzyme inhibitors, angiotensin-receptor blockers, calcium channel blockers, beta blockers, or low-dose thiazides, provided it is stable (ie, no change in drug or dose) for at least 6 weeks prior to enrollment
- For cohorts 6 to 9, use of antiplatelet therapy (low-dose acetylsalicylic acid, clopidogrel or ticagrelor) is allowed, provided subjects have been on a stable dose for at least 6 weeks prior to enrollment and plan to be on the same dose for the duration of the study
- For cohorts 6 to 9, at least 6 subjects in each cohort must be on a stable dose of statin (ie, no change in drug or dose) for at least 6 weeks prior to enrollment and plan to be on the same dose for the duration of the study
- For cohorts 6 to 9, use of ezetimibe is allowed, provided subjects have been on a stable dose for at least 6 weeks prior to enrollment and plan to be on the same dose for the duration of the study
- For cohorts 6 to 9, medication used to manage chronic conditions not excluded by other exclusion criteria, provided subjects have been on a stable dose for at least 6 weeks prior to enrollment and plan to be on the same dose for the duration of the study. Medication must be reviewed

and approved by the investigator, and acknowledged by the Amgen Medical Monitor. Written documentation of this review and Amgen acknowledgement is required for subject participation.

- **For cohort 9, medication used to manage diabetes not excluded by other exclusion criteria, provided subjects have been on a stable dose for at least 6 weeks prior to enrollment and plan to be on the same dose for the duration of the study. Medication must be reviewed and approved by the investigator, and acknowledged by the Amgen Medical Monitor. Written documentation of this review and Amgen acknowledgement is required for subject participation.**

220 Currently receiving apheresis as lipid reducing therapy

221 Subject has known sensitivity to any of the products or components to be administered during dosing

222 Has donated or lost  $\geq$  500 mL of blood or plasma within 60 days of day 1

223 A corrected QT interval (QTc) at screening of  $> 450$  msec in men or  $> 470$  msec in women or history of long QT syndrome

224 History of substance abuse within 12 months before screening

225 Positive test for drugs of abuse at screening or on day -1 for cohorts 1 to 5 or day -3 to -1 for cohorts 6 to 9

226 Use of nicotine or tobacco containing products (including but not limited to: snuff, chewing tobacco, cigars, cigarettes, electronic cigarettes, pipes, or nicotine patches) during the 6 months before screening

227 Unwilling or unable to abstain from nicotine or tobacco containing products (including but not limited to: snuff, chewing tobacco, cigars, cigarettes, electronic cigarettes, pipes, or nicotine patches) throughout the course of the study

228 Subject is unwilling or unable to limit alcohol consumption throughout the course of the study:

- Alcohol is prohibited 48 hours prior to admission to the research facility (day -1 for cohorts 1 to 5 and the sentinel pair of cohort 9; day 1 for cohorts 6 to 9 (other than the sentinel pair) and during the residency periods, and
- Alcohol consumption is limited to no more than 1 drink per day for females and 2 drinks per day for males for the duration of the study (1 drink is equivalent to 12 ounces of regular beer, 8 to 9 ounces of malt liquor, 5 ounces of wine or 1.5 ounces of 80 proof distilled spirits)

229 Subject will not be available for protocol-required study visits or procedures (including the research facility residency period), to the best of the subject's and investigator's knowledge

230 Any other condition that might reduce the chance of obtaining data required by the protocol (eg, known poor compliance) or that might compromise the ability to give informed consent

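### In exclusion criterion 205, one pressure below its limit meets the numeric part of the treated-hypertension exception, while one pressure above the same limit excludes an unmedicated subject

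*Protocol*

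**What the plan says.** Criterion 205 in Protocol Section 7.2 excludes subjects with a clinically significant disorder that, in the opinion of the investigator or the sponsor's medical monitor, "would pose a risk to subject safety or interfere with the study evaluation, procedures or completion. Exceptions include" a list of bullets. The first bullet deals with blood pressure in two sentences.

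- **Medicated subjects.** The exception covers "Subjects with controlled and stable arterial hypertension". Its numeric part reads "with a systolic blood pressure [SBP] < 150 mmHg or diastolic blood pressure [DBP] < 90 mmHg". This has to hold on two occasions, screening and the pre-dose check (day -1 for cohorts 1 to 5, day -3 to -1 for cohorts 6 to 9). Treatment must also be steady: "with no change in medication and dosage for at least 6 weeks prior to enrollment". The same regimen should then continue throughout the study.
- **Unmedicated subjects.** The rule here is "Subjects not on medication are excluded from the study if systolic blood pressure [SBP] > 150 mmHg or diastolic blood pressure [DBP] > 90 mmHg". One such reading on either occasion is enough.

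A repeat rule follows for both groups: a high first reading may be taken again after 15 minutes or more, and the lower value may count.

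The Synopsis and Sections 6.1 and 8.1 state that enrollment in cohorts 1 to 8 is closed. Table 1 plans cohort 9 (675 mg) with 6 subjects on AMG 890 and 2 on placebo.

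**The concern.** The two sentences use the same limits and the same connective, but one grants entry and the other refuses it. In a permission, *or* is lenient: one acceptable pressure is enough. In an exclusion, *or* is strict: one unacceptable pressure is enough. The same pair of readings can therefore lead to opposite numeric results depending only on whether the subject takes antihypertensive medication. Taken alone, the medicated condition also sits badly with the requirement, in the same sentence, that the hypertension be controlled.

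What is at stake is entry to the one cohort still open, which has the highest dose in the study. Its criteria now extend to age 70, BMI 40 kg/m² and well-controlled diabetes (criteria 101, 104 and 205). A site that applies the numbers literally and a site that applies the evident sense of the sentence could decide differently on the same candidate.

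**Working it through.** No figure in the plan needs reproducing. The check applies the two written rules to the same readings.

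**Inputs (Section 7.2, criterion 205).**

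- Medicated subject meets the numeric part of the exception if SBP < 150 or DBP < 90.
- Unmedicated subject is excluded if SBP > 150 or DBP > 90.

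Each pressure can be below, at or above its limit, which gives 3 × 3 = 9 combinations.

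| SBP | DBP | Example | Medicated: numeric part met? | Unmedicated: excluded? | Rules agree? |
|---|---|---|---|---|---|
| < 150 | < 90 | 140/85 | yes | no | yes |
| < 150 | = 90 | 140/90 | yes | no | yes |
| < 150 | > 90 | 140/95 | yes | yes | **no** |
| = 150 | < 90 | 150/85 | yes | no | yes |
| = 150 | = 90 | 150/90 | no | no | **no (reversed)** |
| = 150 | > 90 | 150/95 | no | yes | yes |
| > 150 | < 90 | 160/85 | yes | yes | **no** |
| > 150 | = 90 | 160/90 | no | yes | yes |
| > 150 | > 90 | 160/95 | no | yes | yes |

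Three results follow.

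1. The rules disagree when one pressure is strictly above its limit and the other strictly below. The higher pressure is unbounded: 190/85 and 145/115 also meet the medicated condition and exclude an unmedicated subject.
2. At 150/85 and 140/90 there is no disagreement. The gap opens strictly above the limits.
3. At exactly 150/90 the medicated subject fails the exception, because neither strict inequality holds, while the unmedicated subject is not excluded.

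**Would changing the connective alone be enough?** For comparison only, replace *or* by *and* in the medicated sentence. The disagreements at 160/85 and 140/95 disappear. At 150/85, 140/90 and 150/90 the medicated subject would then fail while the unmedicated subject is not excluded. The mismatch between < and > is thus a second inconsistency that a one-word edit leaves in place.

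**Does other text repair it?**

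- Criterion 219 requires stable antihypertensive medication but sets no pressure limit.
- The repeat-reading rule (criterion 205, Section 10.2.1 and Section 10.3, Vital Signs) applies to both groups and allows the lower reading, so it does not remove the difference.
- Criterion 230 concerns obtaining protocol data and the ability to consent. It adds no pressure limit.
- The opinion clause belongs to the parent exclusion, and the blood pressure bullet is an exception to that exclusion.

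**A sign of a drafting slip.** For the visits, the connective does change between the sentences: the medicated condition applies at screening *and* the pre-dose check, the unmedicated exclusion at screening *or* that check. Those are proper complements. The change was made for timing but not for the pressures.

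**The case against.** The strongest reply is that meeting one number is not the same as being eligible. The conditions of the exception are cumulative: hypertension controlled and stable, the pressure clause at both visits, unchanged medication for at least 6 weeks, and an expectation that it will stay unchanged. An investigator may decline to call a subject at 160/85 controlled. The Synopsis also asks for subjects with no clinically significant abnormality in their medical history. This stands. A reader might infer that the protocol admits subjects with uncontrolled hypertension; the documents support only that such readings meet the numeric part of the exception. What remains is that the protocol defines control by no other measure than the clause in question, so the investigator must either rely on that clause or overrule it.

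A reader might also infer harm to the vital sign endpoint. Vital signs are a primary endpoint (Section 13.1.1.1), but their analysis is descriptive, by visit and as change from baseline (Protocol Section 13.5.2.1.2; SAP Section 9.6.3). No hypothesis test is at risk, and a high but steady baseline does not by itself distort a change from baseline. With 6 active subjects planned, one extreme value could pull a cohort mean, but no figure in the documents shows that this would happen.

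Finally, the sponsor may intend to treat medicated and unmedicated subjects differently. That is possible, but no such intention is stated.

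**Conclusion.** The inconsistency is real and follows from the current text of criterion 205. With one pressure strictly above its limit and the other strictly below, the numeric condition is met for a medicated subject while an unmedicated subject is excluded; at exactly 150/90 the direction reverses. Nothing elsewhere in the protocol resolves this.

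Its reach is limited. Only entry to cohort 9, planned at 8 subjects, can still be affected, and the number of candidates in the gap is unknown. The conclusion assumes that the words are read literally and that the controlled-and-stable phrase, left undefined, may or may not be used to refuse a subject who meets the numeric clause. It does not extend to a claim that uncontrolled subjects are enrolled or that the blood pressure results are compromised. It remains worth correcting because it is an operative, safety-related entry rule whose numeric condition is at odds with its own description of the subject.

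**What to change.** The two sentences of the blood pressure bullet must be reconciled in three respects:

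- the connective between systolic and diastolic pressure in the medicated exception;
- the handling of values exactly at the limits, where the sentences now use < and > respectively;
- the agreement of the numeric condition with the requirement that hypertension be controlled and stable.

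Alternatively, if medicated and unmedicated subjects are meant to face different numeric rules, the protocol should say so. The choice of limits, and of the rule for each group, is the sponsor's; this point takes no view on it.

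The cost is a few words of eligibility text in an amendment, which needs ethics approval (Sections 14.2 and 15.1), and the possible loss of a few cohort 9 candidates. Sample size, visit schedule and analysis are unaffected.
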